## **23 Appendix B: Extended Follow-Up of Successful Aging Participants after Delivery of the Hearing Intervention**

*Note: The Hearing Intervention participants are already being offered extended follow-up as part of a separate trial (Randomized Trial of Telehealth vs. Conventional Hearing Care Delivery in the ACHIEVE Study [ACHIEVE-HIFU]; R01DC019408; IRB00284937 [JHU sIRB]).*

### **23.1 Background and rationale**

As part of participation in the ACHIEVE trial, upon completion of the final Year 3 visit, participants are offered the intervention that they were not initially randomized to receive (i.e., participants who were randomized to receive the hearing intervention program are offered the successful aging education program, and vice versa – see section 22 Appendix A: Delivery of the Other Intervention after Completing ACHIEVE Trial). For the successful aging participants who receive the hearing intervention program after Year 3, we would like to learn how receiving hearing aids affects the participants' hearing and communication, as well as social, mental, physical, and overall well-being. We also want to understand how much participants use their hearing aids and the hearing care support from the study audiologists, as well as the modality of hearing care support (telehealth vs. in-person).

### **23.2 Participants**

To be eligible for the extended follow-up, participants must:

- 1) have been eligible for and participated in the successful aging intervention arm of the ACHIEVE trial,
- 2) agree to receive the hearing intervention program, and
- 3) be able and willing to participate in this extended follow-up (i.e., provide separate consent for the extended follow-up).

ACHIEVE participants who have developed cognitive impairment are eligible for the extended follow-up visits if they are willing to participate and are consented with a proxy (see section 6.1 Informed consent).

### 23.3 Schedule of activities

	42-month	Year 4
Informed consent	X a	
Hearing Intervention		
SA Intervention check-up	X	X
International Outcome Inventory for Comprehensive Hearing Intervention	X	X
Audiometry		
Air conduction audiometry		X
Bone conduction audiometry		X b
Tympanometry		X
Word Recognition in Quiet		X
Quick Speech in Noise (unaided)		X
Social, Mental, and Physical Outcomes		
CES-D Scale	X	X
Hearing Handicap Inventory for the Elderly - Screening Version	X	X
RAND-36 Health Survey	X	X
Cohen Social Network Index	X	X
UCLA Loneliness Scale	X	X
Hospitalizations	X	X
Qualifying (S)AE assessment	X	X
Abbreviated neurocognitive battery c	X	
Full neurocognitive battery d		X
Clinical Dementia Rating Scale - Participant (CDP)		X
Dementia/MCI evaluation if applicable (CDI, CDS, NPI)		X b
Baecke activity questionnaire		X
Falls and mobility questionnaire		X
Accelerometry		X
Grip strength		X
Short Physical Performance Battery		X
Covariates		
Health history		X
Neurologic history		X
Anthropometry		X
Seated blood pressure		X
COVID impact questionnaire	X	X
Telehealth acceptance post-intervention (TAF)	X	X

aInformed consent can occur following the ACHIEVE Year 3 visit, at Hearing Intervention Session A, or at the 42-month visit prior to any data collection.

bProcedures that are intermittent based on protocol.

cEnsuring Speech Understanding (ESU) and MMSE only.

dESU, MMSE, Delayed Word Recall Test, Digit Symbol Substitution Test, Incidental Learning, Trail Making Test Part A and Part B, Logical Memory I and II, Digit Span Backward, Boston Naming Test, Word Fluency (FAS), and Animal Naming.

### 23.4 Procedures

See section 7 Data collection and measurements for descriptions of all procedures, except for the telehealth acceptance questionnaire post-intervention. The telehealth acceptance post-intervention questionnaire (TAF) is an interviewer-administered questionnaire that assesses the

participant's comfort with and acceptance of telehealth hearing health care after starting the telehealth intervention.

As part of participation in this extended follow-up, participants will be able to continue receiving hearing follow-up care from the study audiologist (e.g., maintenance, adjustments, counseling, monitoring of listening goals) for an additional 6 months beyond what was covered as part of the delivery of the other intervention (i.e., for 1 year after receiving the hearing aids). For each participant issue, the audiologist will document the modality of support provided (e.g., telephone, video call, clinic visit, hybrid), the number and duration of the encounters, the type of issue, and its resolution.

### **23.5 Safety**

As only one questionnaire (TAF) has been added vs. what was collected in the main ACHIEVE trial, there are no new risks associated with extended follow-up.

STATISTICAL ANALYSIS PLAN: ACHIEVE

PROTOCOL:	Aging and Cognitive Health Evaluation in Elders (ACHIEVE) Randomized Trial
GRANT Number	R01AG055426
NCT Number	NCT03243422
SAP VERSION	5.2
SAP DATE:	February 23, 2023
PROTOCOL DATE:	November 9, 2021 (V.1.10)
SPONSOR:	National Institute on Aging
PREPARED BY:	Collaborative Studies Coordinating Center Department of Biostatistics University of North Carolina at Chapel Hill
AUTHORS:	Will be listed in order of contribution as draft is prepared

REVISIONS HISTORY:

Version	Author	Date	Description
1	[name], [name]	9/4/20	Original SAP
2	[name], [name], [name]	4/15/21	Updated SAP due to COVID 19
3	[name], [name], [name]	8/20/21	Additional updated due to COVID 19
4	[name], [name], [name]	3/14/22	Details added to clarify analytic plan
5	[name], [name], [name]	4/27/22	Noted in section 7.5 that results from the analysis of secondary outcomes will be included in primary outcome manuscript
5.1	[name], [name], [name]	11/11/22	Minor Update: Clarified definition of secondary outcome and described sensitivity analyses.
5.2	[name], [name], [name]	2/23/23	Minor Update: Clarified use of Hochberg modification to the Bonferroni adjustment.

Changes from version 1.0 to 2.0

Affected section	Brief description of change	Brief rationale for change
4. Study Design	Added: Each participant will be followed for 36 months; the COVID-19 pandemic made in person visits impossible from mid-2020 to mid-2021 delaying the closeout 36 month visit for many participants.	Due to COVID-19
4. Study Design	Added: Four intervention visits occur every three weeks following randomization. Routine follow-up clinic visits occur every six months until month 36. The purpose is to gather measures of primary and secondary outcomes. Starting in April 2020, remote data collection of primary and secondary outcomes became necessary due to the coronavirus pandemic (see section 7.1 for description of alternative modes of data collection). In January 2021, due to the coronavirus pandemic, it was decided participants' final study visit will be a split visit that will comprise first a phone- based component AND later an in-person component (with final cognitive assessment and receipt of the other study intervention) that will be conducted once field site clinics reopen in the future.	
7.1 General Considerations	Removed the third mode of neurocognitive data collection (Video Conferencing). Updated the calibration analysis and noted that factor analysis will be performed using MPlus 8.6 or later	It was decided not to use the video conferencing for neurocognitive data collection during COVID-19
7.3 Primary Analysis	Updated to note if a nonlinear trend is observed, the model will be adapted to include time splines. Updated the covariates to sex, race-center, and education, Cohort type (ARIC vs De novo. Removed the word "ANCOVA" from all covariates included in the ANCOVA model	Due to COVID-19 neurocognitive collection will be over the phone until in- person visits can resume
7.4 Sensitivity Analyses of the Primary Outcome	Updated one of the sensitivity analyses to look at cognitive decline based on a categorized version of time (visit) rather than continuous time in years	Due to COVID-19 the amount of follow- up time will be longer than 3 years for some participants.

7.6 Exploratory	Updated the Exploratory analysis looking	Due to COVID-19
Analyses of the	at whether or not the intervention alter	
Primary Outcome	the trajectory of cognitive decline	
10. COVID-19	Added information regarding conducting	Due to COVID-19
	the year 3 visit as a split visit.	

Changes from version 2.0 to 3.0

Affected section	Brief description of change	Brief rationale for change
7.1 General	Updated administration of the	Due to COVID-19
Considerations	neurocognitive assessment to note in-	
	person visits resumed in June 2021.	
	Removed the paragraph on calibration.	
7.3 Primary	Noted that we will be using both the in-	Due to COVID-19
Analysis	person and telephone based	
	neurocognitive assessments.	
7.4 Sensitivity	Added a new Sensitivity analysis "An	Due to COVID-19
Analyses of the	analysis of a co-calibrated ^{10,11} global	
Primary Outcome	cognitive function factor scores in which	
	the ten tests administered in-person and	
	the six tests administered over the phone	
	will be included in the confirmatory	
	factor analysis model. Modeling	
	constraints will be applied to scale the	
	co-calibrated factor score to the same	
	metric as the in-person factor score	
	utilized in the primary analysis ²¹ . Mode	
	of data collection (in-person, phone) will	
	be included in the analytic model as a	
	covariate."	
7.5 Key Secondary	Clarified which secondary outcome	Due to COVID-19
Outcomes	would be consider the main and	
	elaborated the definitions.	

Changes from version 3.0 to 4.0

Affected section	Brief description of change	Brief rationale for change
7.1, General	Added threshold for dichotomization of	Clarified how hearing loss would be
Considerations and	hearing loss and removed the ambiguous	defined as a covariate in the primary
7.3 Primary	term "stratum".	analysis.
Analysis		
7.1 General	Removed phone-based cognitive scores	A test of 35 separate models revealed that
Considerations	and added race to the imputation model.	phone-based global cognitive function
7.3 Primary	Removed the sentence "The phone-based	factor scores did not improve the
Analysis	global cognitive function factor score	performance of the imputation model.
	will be included in the imputation model	However, adding race as an auxiliary
	as an auxiliary variable."	variable resulted in a small improvement.

7.3 Primary	For the primary analysis the time scale	Clarified the timeframe for cognitive
Analysis	was specified as "years from the	decline.
	baseline."	

Changes from version 4.0 to 5.0

Affected section	Brief description of change	Brief rationale for change
7.5 Secondary	Clarified that results from the analysis of	Specified the importance of examining
Outcomes	secondary outcomes will be included in	intervention effects on both cognitive
	the primary outcome manuscript	decline and adjudicated dementia.

Changes from version 5.0 to 5.1

Affected section	Brief description of change	Brief rationale for change
7.5 Secondary	Clarified definition of secondary outcome	Specified source of information for
Outcomes	and described sensitivity analyses.	adjudicated MCI and dementia.

Changes from version 5.1 to 5.2

Affected section	Brief description of change	Brief rationale for change
7.7 Adjustment for	Clarified use of Hochberg modification	Specified that the Hochberg modification
Multiple	to the Bonferroni adjustment.	to the Bonferroni adjustment will be
Comparisons		applied to five outcomes (1) decline in
		global cognitive function, (2) time to
		incident cognitive impairment, (3)
		decline in memory domain, (4), decline
		in executive function domain, and (5)
		decline in language domain.

SAP Signatures

DSMB Board and National Institute on Aging	June 2, 2022
Principal Investigator – [name], PhD	May 16, 2022
Protocol Statistician – [name]	May 16, 2022

TABLE OF CONTENTS

1.	Int	roduction	7
2.	Ba	ckground	7
3.	Ob	jectives	7
4.	Stu	ıdy Design	7
4.	.1	Inclusion Criteria	8
4.	.2	Exclusion Criteria	9
5.	Pov	wer	9
5.	.1	Preliminary Analysis	9
5.	.2	Evaluation of Assumptions 1	0
6.	An	alysis Populations1	0
6.	.1	Intent-to-Treat Population	0
6.	.2	Per Protocol and Complier Population	1
7.	Sta	tistical Analysis1	1
7.	.1	General Considerations	1
7.	.2	Primary Outcome 1	2
7.	.3	Primary Analysis 1	3
7.	.4	Sensitivity Analyses of the Primary Outcome	3
7.	.5	Secondary Outcomes	4
7.	.6	Exploratory Analyses of the Primary Outcome 1	4
7.	.7	Adjustment for Multiple Comparisons1	5
7.	.8	Additional Outcomes1	5
8.	Glo	obal cognitive function factor score1	5
9.	CC	VID-19 Considerations	6
10.	Sot	ftware and Statistical Programming1	6
11.	Re	ferences 1	6

LIST OF ABBREVIATIONS

ACTIVE	Advanced Cognitive Training for Independent and Vital Elderly study
AD	Alzheimer's Disease
APOE	Apolipoprotein E
ARIC	Atherosclerosis Risk in Communities
CDR	Clinical Dementia Rating
dB	decibels
DSMB	Data and Safety Monitoring Board
HealthABC	The Health, Aging, and Body Composition Study
HRQL	Health-Related Quality of Life
ITT	Intention-to-treat
MCI	Mild Cognitive Impairment
MMSE	Mini-Mental State Exam
SD	Standard deviation

1. Introduction

ACHIEVE is a randomized controlled trial. Approximately 850 participants will be randomly assigned to one of two conditions and followed for three years: hearing intervention with hearing aids or successful aging intervention. Participants will be community-dwelling adults aged 70-84 years with audiometric hearing impairment defined as a four-frequency (0.5, 1, 2, 4 kHz) pure-tone average threshold in the better-hearing ear of \geq 30 decibels (dB) and <70dB. This document gives details of the planned statistical analyses.

2. Background

Novel approaches for reducing cognitive decline in older adults are needed given the aging of the population and the personal, socioeconomic, and public health implications of cognitive impairment and dementia in older adults. Epidemiologic data now strongly suggest that age-related peripheral hearing loss in older adults is independently associated with accelerated cognitive decline and incident dementia¹⁴. Mechanistic pathways that could underlie this observed association include the effects of poor audition and distorted peripheral encoding of sound on cognitive load, brain structure, and/or reduced social engagement. These pathways may be amenable to comprehensive hearing rehabilitative treatment consisting of the use of hearing assistive technologies (hearing aids, other integrated hearing assistive devices) and rehabilitative training. To date, however, there has never been a randomized trial that has investigated whether hearing loss treatment could reduce cognitive and other functional declines in older adults.

3. Objectives

The main objective of ACHIEVE is to determine the effect of a hearing intervention versus a successful aging control intervention on the primary outcome of global cognitive decline in 70-84 year-old well-functioning and cognitively-normal adults with hearing loss. An important secondary outcome is time until cognitive impairment (defined in section 7.5). Additional secondary outcomes include decline in the cognitive domains of memory, executive function, and language. Changes in social and physical function, physical activity, and health-related quality of life (HRQL) will be examined in exploratory analyses.

Additional exploratory objectives in ACHIEVE include: 1) to investigate whether the hearing intervention alters within-individual pre- to post-intervention trajectories of cognitive decline in the subgroup of participants recruited from the Atherosclerosis Risk in Communities (ARIC) cohort who have been followed for ~30 years prior to enrollment in the ACHIEVE trial; and 2) to evaluate the effect of hearing intervention on rates of cognitive decline in individuals with different demographics, biomarkers, and Alzheimer's disease risk factors.

4. Study Design

ACHIEVE is a randomized, open-label trial comparing a hearing intervention versus a successful aging control intervention. The original plan for enrollment was to recruit 850 participants with approximately 425 in each condition. The final enrollment was expanded to 977 participants following a sample size assumption analysis (see section 5.2) conducted in June 2019. Enrollment began in November 2017. Each participant will be followed for 36 months; the COVID-19 pandemic made in-person visits impossible from mid-2020 to mid-2021 delaying the closeout 36 month visit for many participants.

Participants in the hearing intervention condition are fitted with a hearing aid, instructed to be worn on a daily basis for study duration, and attend four 1-hour intervention sessions spaced over the 2-3 months post-randomization. Re-instruction in use of devices and hearing rehabilitative strategies will be provided every 6 months.

The successful aging control intervention consists of four 1-hour intervention sessions spaced over the 2-3 months post-randomization focusing on participant-selected topics from the 10 KeysTM to Healthy Aging program and upper body stretching. Additional sessions will be provided every 6 months.

When spouses or cohabitating partners are both eligible and randomized together, they will be randomized as a unit with, arbitrarily, the first spouse/partner of the pair to be selected according to the random assignment procedure and the second spouse/partner of the pair receiving the same assignment. Spouse/partner pairs will be randomized in spouse/partner-pair specific permuted order blocks of varying sizes within strata defined by participant status (at least one spouse/partner pair in ARIC or both non-ARIC participants) and by field site.

Pre-screening will determine if an individual meets the inclusion criteria. The screening visit is used to consent participants and to determine if an individual meets audiometric, vision, and cognitive inclusion criteria. During the baseline visit assessments measures of primary and secondary outcomes will be collected.

Four intervention visits occur every three weeks following randomization. Routine follow-up clinic visits occur every six months until month 36. The purpose is to gather measures of primary and secondary outcomes. Starting in April 2020, remote data collection of primary and secondary outcomes became necessary due to the coronavirus pandemic (see section 7.1 for description of alternative modes of data collection). In January 2021, it was decided participants' final study visit will be a split visit that will comprise a phone-based component AND a subsequent in-person component (with final cognitive assessment and receipt of the other study intervention) that will be conducted once field site clinics reopen following closures prompted by the coronavirus pandemic.

4.1 Inclusion Criteria

To be eligible for the study, participants must meet all of the following criteria:

- Age 70-84 years at the time of randomization. This age range will allow recruitment of participants who are at risk for cognitive decline but who may also be expected to survive for the duration of the study.
- Community-dwelling.
- Fluent English-speaker.
- Residency. Participants must plan to reside in the local area for the study duration.
- Audiometric hearing impairment. Participants must have adult-onset hearing impairment with a four-frequency pure tone average (0.5, 1, 2, 4 kHz) in the better-hearing ear of ≥ 30 decibels and <70dB. This level of hearing impairment is the level at which individuals would be most likely to benefit from the use of conventional amplification devices such as hearing aids.
- Word recognition in quiet score ≥60% in better ear. A word recognition in quiet score <60% suggests hearing impairment that is too severe to benefit from conventional amplification devices such as hearing aids.
- Mini-Mental State Exam (MMSE) score ≥ 23 for individuals with high-school degree or less; MMSE score ≥ 25 for individuals with some college or more; Participants must be at risk for cognitive decline in the range quantified well by neurocognitive testing, and so must be free from more substantial cognitive impairment at baseline.

Participants must be willing and able to consent to participate in the study, be willing to be randomized to either the hearing intervention or to the successful aging control intervention and be willing to commit to adhere to the protocol for the duration of the study.

4.2 Exclusion Criteria

Potential candidates for enrollment who meet one or more of the following criteria are excluded from participation in the study:

- Self-reported disability in ≥ 2 or more Activities of Daily Living.
- Any self-reported hearing aid use in the past year. Participants will be randomized to hearing intervention or successful aging control intervention and, therefore, participants cannot already be receiving treatment for their hearing loss.
- ARIC participants only: Diagnosis of adjudicated dementia based on a previous ARIC visit or participant required a proxy to assist with completing informed consent and responding to questions at ARIC visit 6 or 7.
- Vision impairment (worse than 20/40 on MN Near Vision Card). Participants who cannot see (with correction) well enough to complete the neurocognitive assessment are excluded.
- Medical contraindication to use of hearing aids (e.g., draining ear). Because hearing aids will be the primary device used in the hearing intervention, participants with medical contraindications to hearing aid use are excluded.
- Conductive hearing impairment as determined by a difference in air audiometry and bone audiometry ("air-bone gap") greater than 15 dB in 2 or more contiguous frequencies in both ears. Because the impact of a conductive (versus a sensorineural) hearing loss on cognitive functioning may potentially differ and programming for hearing aids differs for conductive hearing loss, participants with permanent conductive hearing loss are excluded from the study. Participants with an air-bone gap due to fluid in the ears or other resolvable medical issue may be enrolled in the study following successful medical resolution of the cause of the air-bone gap.
- Unwilling to wear hearing aids on a regular (i.e., daily or near daily) basis.
- No participants are excluded based on race or sex.

Temporary Exclusion Criteria: Participants determined to have a conductive hearing impairment as measured by a difference in air audiometry and bone audiometry ("air-bone gap") greater than 15 dB in 2 or more contiguous frequencies in both ears are excluded from the study and referred for medical follow-up. Should the cause of the air-bone gap be determined to be due to a temporary or treatable medical issue (e.g., fluid or wax in the ears), participants may be enrolled following resolution of the issue (i.e., air-bone gap). Participants with asymmetrical sensorineural hearing (\geq 20 dB at 2 adjacent frequencies or \geq 10 dB at 3 adjacent frequencies) or with other symptoms/signs concerning for a retrocochlear etiology based on the assessment of the audiologist will also not be eligible to participate until a medical clearance/evaluation is obtained.

5. Power

5.1 Preliminary Analysis

Data from the ARIC cohort, the Advanced Cognitive Training for Independent and Vital Elderly (ACTIVE) randomized trial, and the Health Aging and Body Composition (HealthABC) study were utilized to estimate that in the absence of an intervention a factor score (described in section 8.0) of global cognitive function would decline at a rate of 0.08 standard deviations (SDs) per year with a variability of 0.09 SDs. These estimates of the slope and variance were translated into expected values at Year 3. Power was conservatively estimated using a simplified t-test approach, while recognizing that greater power would be provided in the analysis of the primary outcome of cognitive decline through the application of repeated measures mixed effects models (described in section 7.3). The original sample size for ACHIEVE was 850, which provided greater than 90% power to detect a 35% difference in annual cognitive decline (Intervention: -0.052, Control: -0.08) with a 2-sided test and p < 0.05.

Attrition due to withdrawal or mortality was estimated at 10% per year, corresponding to 27.1% over 3 years. This is a conservative estimate given that *total* attrition in ACHIEVE is 6.7% as of October 6th, 2021. The drop-in/drop-out rate was estimated at 15% over 3 years. This rate reflects participants in the successful aging control condition who begin to wear hearing aids (drop-in) and participants in the hearing intervention condition who stop wearing hearing aids (drop-out). As of October 6th, 2021 there are 46 participants in the control condition who are currently using hearing aids (9.4% drop-in) and 8 participants in the intervention condition who are not currently using hearing aids (1.6% drop-out). After accounting for a 15% drop-in/drop-out rate, the difference at Year 3 was reduced to 29% (Intervention: -0.057, Control: -0.08). With an attrition rate of 10% per year, the initial sample size for ACHIEVE provided greater than 80% power to detect a difference utilizing a 2-sided t-test and p < 0.05.

For the secondary outcome of incident cognitive impairment, a dataset was constructed of participants in the ARIC cohort who had comparable characteristics to the individuals enrolled in ACHIEVE, did not exhibit signs of cognitive impairment at the baseline, and who were monitored over a period of 5 to 8 years. The observed rate was 50 cases of incident cognitive impairment per 1000 person-years. Assuming a 30% reduction in the hearing intervention condition and a 25% loss of person-time due to attrition, the proposed proportional-hazards model (described in section 7.5) would have 80% power to detect a hazard ratio of 0.54 when using a 2-sided test and p < 0.05.

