drop-in and drop-out rates low (e.g., rigorous training for active group vs. energized successful aging group promised free hearing aids at trial completion). Among 13 participants in the ACHIEVE-Pilot study who were randomized to the hearing intervention and have since been followed to 1 year, we did not observe any drop-out (discontinuation of hearing aid use) at 1 year (12 participants reported > 8 hours of hearing aid use/day and 1 participant reported 4-8 hours use/day). Similarly, drop-in rates will likely be minimized because all participants in the successful aging group are informed that they will receive free hearing intervention after 3 years of follow-up (out-of-pocket costs for hearing aids are otherwise currently ~\$4700 and are rarely covered by insurance). Rates of uptake of hearing aid use remain low in the community. In the HealthABC study among individuals with hearing loss in the inclusion range for the ACHIEVE study, rates of hearing aid uptake were ~3-4% per year.

- Missing data/withdrawal from competing events (e.g., mortality not associated with dementia): Estimated at 10%/year (corresponding to 27% in 3 years)

Based on these parameters and with 850 total individuals randomized, we will have 90% power to detect a 35% difference in annual cognitive decline between the hearing intervention vs successful aging intervention at 3 years follow-up.

**Aim 2:** For the secondary outcome of incident cognitive impairment, a dataset was constructed of participants in the ARIC cohort who had comparable characteristics to the individuals enrolled in ACHIEVE, did not exhibit signs of cognitive impairment at the baseline, and who were monitored over a period of 5 to 8 years. The observed rate was 50 cases of incident cognitive impairment per 1000 person-years. Assuming a 30% reduction in the hearing intervention condition and a 25% loss of person-time due to attrition, the planned analysis would have 80% power to detect a hazard ratio of 0.54 when using a 2-sided test and  $p < 0.05$ .

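### SAP 5.1 and Protocol 12.1 assume a 30% reduction in incident cognitive impairment but give power only for a hazard ratio of 0.54; power at the assumed 0.70 is about 36% on the stated inputs and is not reported

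*SAP*

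**What the plan says.** The last paragraph of SAP 5.1 sets out the planning for the secondary outcome of incident cognitive impairment. The control rate comes from a comparable ARIC subset: "The observed rate was 50 cases of incident cognitive impairment per 1000 person-years". The planning assumptions are "Assuming a 30% reduction in the hearing intervention condition and a 25% loss of person-time due to attrition". The conclusion is that the proportional-hazards model "would have 80% power to detect a hazard ratio of 0.54 when using a 2-sided test" at the 0.05 level.

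Protocol 12.1, Aim 2, uses the same inputs and reaches the same result: "the planned analysis would have 80% power to detect a hazard ratio of 0.54".

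Neither paragraph says how the 30% and the 0.54 are related, and neither gives power at a 30% reduction. SAP 5.2 and Protocol 12.4 later report 80% power at HR 0.60 for the 977 enrolled, again without a figure for the 30% reduction.

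**The concern.** A 30% reduction is an HR of 0.70. An HR of 0.54 is a 46% reduction. The paragraph therefore names one effect as its planning assumption and reports power for a much larger one.

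Two things follow. The power at the only effect that the documents assume is missing. The 80% also appears to rest on two hazard ratios at once, one to count events and another as the effect.

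SAP 7.5 calls the composite an important secondary outcome and sends its result to the primary manuscript, and SAP 7.7 tests it under a Hochberg procedure. Without power at the planning effect, a reader cannot judge how informative a non-significant result would be.

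**Working it through.** **Inputs**
- Participants: 850, about 425 per arm (SAP 4: "The original plan for enrollment was to recruit 850 participants with approximately 425 in each condition"); 977 finally enrolled (SAP 5.2). The impairment paragraph does not restate the sample size.
- Follow-up: 3 years (SAP 4).
- Control rate: 0.050 per person-year (SAP 5.1).
- Person-time: "a 25% loss of person-time due to attrition" (SAP 5.1).
- Two-sided 0.05, so z = 1.960; z for 80% power = 0.8416; sum 2.8016.

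**Formulas**
- Events = (N/2) × 3 × (1 − loss) × 0.05 × (1 + HR).
- Power (Schoenfeld, 1:1) = Φ(|ln HR| × √events / 2 − 1.960).
- Detectable HR at 80% power = exp(−2 × 2.8016 / √events).

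**1. Reproducing the plan's figure**
- Person-years per arm: 425 × 3 × 0.75 = 956.25.
- Events under HR 0.70: 956.25 × (0.050 + 0.035) = 81.3.
- Detectable HR: exp(−5.603 / 9.016) = 0.537, which rounds to 0.54.
- Power at HR 0.54 with 81.3 events: Φ(0.616 × 9.016 / 2 − 1.960) = 79.3%.

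The documents do not show their calculation, so this is a reconstruction. The variants tried do not round to 0.54: Freedman's formula gives 0.526, exponential depletion of person-time 0.529, a 27.1% loss 0.532, the control rate in both arms 0.564 and a one-sided test 0.576.

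**2. One hazard ratio throughout, N = 850**
- Events under HR 0.54: 956.25 × (0.050 + 0.027) = 73.6.
- Power: Φ(0.616 × 8.581 / 2 − 1.960) = 75.3%.
- Setting power to 80% and solving with the event count tied to the same HR gives 0.518.

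**3. Power at the assumed HR 0.70** (|ln 0.70| = 0.3567)

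| N | Loss of person-time | Events | Power |
|---|---|---|---|
| 850 | 25% | 81.3 | 36.2% |
| 977 | 25% | 93.4 | 40.7% |
| 977 | 6.7% | 116.2 | 48.5% |
| 977 | none | 124.6 | 51.2% |

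The 6.7% is the total attrition that SAP 5.1 reports as of October 2021. Using it as a loss of person-time is an assumption. 80% power at HR 0.70 needs 247 events, or 247 / (3 × 0.75 × 0.0425) = about 2,583 participants on the stated inputs.

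**4. The later HR 0.60, N = 977**
- With events counted under HR 0.70, as in step 1, the detectable HR is 0.560 at 25% loss, 0.595 at 6.7% and 0.605 with no loss.
- With HR 0.60 throughout and 25% loss: 488.5 × 2.25 × 0.05 × 1.60 = 87.9 events and 66.8% power.
- With HR 0.60 throughout and no loss: 488.5 × 3 × 0.05 × 1.60 = 117.2 events and Φ(0.511 × 10.83 / 2 − 1.960) = about 79%.
- So 0.60 is approached only with little or no loss of person-time. SAP 5.2 does not say which loss it used.

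**The case against.** The strongest defence is that 0.54 is a legitimate minimum detectable HR: fix the expected events under a planning assumption, then solve for the effect that gives 80% power. Much of this stands. The figure reproduces, so it is not a slip of arithmetic, and mixing the two hazard ratios moves power by only about four points (79.3% against 75.3%). What remains is that neither document says the 30% served only to count events, and a detectable HR whose event count assumes a different HR is not self-consistent.

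A reader might infer that the plan claims 80% power at a 30% reduction. It does not: the HR of 0.54 is printed beside the power.

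A reader might also take 36% as the power of the trial that was run, so that a true 30% reduction would be missed nearly two times in three. The documents do not support that. The 36% belongs to the planned 850 at 25% loss. Enrolment was 977, SAP 5.1 calls its attrition assumption conservative, and SAP 9 notes that some participants have more than 36 months of follow-up.

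Nor can these figures be assigned to the composite itself. The rate of 50 per 1000 is for impairment in ARIC, whereas the composite in SAP 7.5 also counts 3-point drops on the MMSE or a phone-based equivalent, and no rate is given for it. With assumed control rates, 977 participants and 6.7% loss, power at HR 0.70 would be about 49% at 50, 65% at 75 and 78% at 100 per 1000 person-years. At 25% loss, 80% power would need about 132 per 1000: 247 / (1099.1 × 1.70) = 0.132.

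Finally, this is a secondary outcome and no analysis depends on the figure. That limits the weight of the point but does not remove it.

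**Conclusion.** The concern holds as a matter of incomplete and inconsistent power reporting. SAP 5.1 and Protocol 12.1 assume HR 0.70 and report power only at HR 0.54, using an event count from the former. On one consistent HR with 850 participants, power at 0.54 is about 75%, and 80% is reached at 0.52. At the assumed HR 0.70, power is about 36% with 850 participants, and between about 41% (25% loss) and 51% (no loss) with 977.

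These results rest on 3 years of follow-up, a control rate of 50 per 1000 person-years, 1:1 allocation and unadjusted two-sided 0.05. Rejection under the Hochberg procedure in SAP 7.7 requires a p-value below 0.05, so on the same inputs they are upper bounds for that test. They would rise if the composite's event rate exceeds the ARIC rate. Power for the primary outcome is untouched.

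**What to change.** In SAP 5.1 and Protocol 12.1 (Aim 2):
- Label the HR as a minimum detectable value and compute it with one hazard ratio throughout: 80% power at HR 0.52, or about 75% power at HR 0.54, for 850 participants.
- State power at the assumed HR 0.70 together with its inputs: about 36% with 850 at 25% loss, and about 41% to 51% with 977 for losses from 25% to none.
- Note that these figures use unadjusted 0.05 and the ARIC impairment rate, and that no event rate is available for the composite.

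In SAP 5.2 and Protocol 12.4, restate the HR 0.60 on the same basis and name the loss of person-time behind it, so that the sections agree.

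The analysis in SAP 7.5 needs no change. The cost is a few restated figures, less favourable than those now printed; there are no further participants or data, and no analysis changes.
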